**Abstract:**

This is a randomized clinical trial from March 28st 2019 to March 28st 2024. The purpose of this study is to evaluate the survival benefits of statins in breast cancer patients with abnormal lipid metabolism. Consecutive samples will be enrolled based on inclusion and exclusion criteria. They will be grouped randomly into intervention group or control group after informed consent. A third group independent from research team will be in charge of randomization. In this study, 348 patients were randomly divided into two groups according to patients' wishes and written informed consent. The experimental group: control group = 1:1. Patients in both groups will undergo breast cancer treatment. The experimental group used statins, while the control group used dietary intervention instead of statins. The main endpoint was 5 years DFS. The subjects were breast cancer patients. For statistical analysis, t-test will be used between two different groups. Estimated sample size will be calculated using t-test. Log rank test was used with survival curve based on Kaplan Merier method and 95% confidence interval of median survival time. Data and Safety Monitoring Board will periodically review, evaluate and give recommendations to this study in various aspects.

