## **Methods:**

### Overview of design:

A randomized, open, blank controlled, single-center clinical trial was conducted to compare the survival benefits of statins in breast cancer patients with dyslipidemia (low and medium risk of ASCVD). The control group used dietary intervention instead of statins. The main endpoint was 5 years DFS. The subjects were breast cancer patients. In this study, 348 patients were randomly divided into two groups according to patients' wishes and written informed consent. The experimental group: control group = 1:1. Subjects were screened and administered continuously until the disease progressed and the toxicity was intolerable. Informed consent was withdrawn or the researcher decided that the drug must be discontinued.

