#### Plans for sampling, recruiting and retaining subjects:

- Sample type: Convenience sample
- Sampling procedures: Convenience sampling will be used to enroll a cohort of breast cancer patients with dyslipidemia (low and medium risk of ASCVD), and randomly separate them into two groups. We prepare to use SPSS software to do the randomly separation. Experimental group used statins, the other one used dietary intervention instead of statins.
- Recruitment method: When patients presented our hospital diagnosed of breast cancer with dyslipidemia (low and medium risk of ASCVD), we will review these patients' medical records to find out the potential subjects for this study according to the inclusion and exclusion criteria. The eligible subject who is willing to participate in this study will be enrolled and consented. They will be randomly (using SPSS software) divided into 2 groups. One is statins group, the other one is control group.

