#### Measurements:

- Predictor variables:

The predictor variable we are assessing is whether use statins. According to which, we established the intervention group and control group.

- Outcome variables:

The primary outcome: DFS (disease free survival) rate

Secondary outcome: OS (overall survival) rate

- Potential confounders:

Since this protocol is an RCT (randomly clinical trial) on survival benefits between statins group and control group, it will balance the confoundings in it, such as age, slight pathology difference, tumor size difference, lymph node status difference, tumor grade difference, and the different surgeons between the 2 groups.

- Plans for randomization, blinding, run-in period as needed:

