### **Data safety & monitoring:**

The members of DSMB are 3 professors in the breast surgery department, 6 attending doctors and 3 residents. DSMB members will meet:

- 1) before the start of the trial to discuss the study protocol,
- 2) at early stage of about 10-20 patients are enrolled. In order to monitor **enrollment** efficacy, **adverse effects** that might have happened, the efficacy of **blinding** strategy, the current **outcome variables** in control and interventional group (only known to DSMB members), **protocol** compliance and quality control issues.
- 3) Subsequent DSMB meetings will be hold regularly (at least every three months) or anytime when there are safety issues, need to stop the program earlier and so on.

If DSMB find that the statins are causing harm, they could discuss whether to end the study early after balancing between ethical responsibility to the participants and the advance of scientific knowledge.

If DSMB find that the statins are much more effective than anticipated, they could stop the study before the primary endpoint.

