LDL-C\_\_\_\_\_TC\_\_\_\_\_TG\_\_\_\_\_ALT\_\_\_\_\_CK\_\_\_\_\_Fatty Liver\_\_\_\_\_

5 year follow-up: date\_\_\_\_\_statin\_\_\_\_\_

LDL-C\_\_\_\_\_TC\_\_\_\_\_TG\_\_\_\_\_ALT\_\_\_\_\_CK\_\_\_\_\_Fatty Liver\_\_\_\_\_

RT (recurrence time)\_\_\_\_\_

Other event\_\_\_\_\_

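### The trial is dated exactly five years with staggered entry, yet its main endpoint is 5-year DFS; dates and endpoint conflict on the plain reading, and no data cut-off is stated

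*Combined protocol and SAP*

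**What the plan says.** **Dates.** Abstract: "This is a randomized clinical trial from March 28st 2019 to March 28st 2024".

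**Entry.** Abstract: "Consecutive samples will be enrolled based on inclusion and exclusion criteria". The section on sampling, recruiting and retaining subjects has patients identified as they come to the hospital: "When patients presented our hospital diagnosed of breast cancer with dyslipidemia". Data safety & monitoring ties one board meeting to a point in enrolment: "at early stage of about 10-20 patients are enrolled". Entry is therefore staggered, though the plan does not use that word.

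**Endpoint.** Overview of design (and the Abstract): "The main endpoint was 5 years DFS". Measurements gives no time point: "The primary outcome: DFS (disease free survival) rate". The case form in the Appendix runs to "5 year follow-up: date", and that block has a recurrence-time field.

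**Tests.** Abstract: "For statistical analysis, t-test will be used between two different groups". The Abstract also says that the sample size comes from a t-test, and then names a log-rank test with Kaplan-Meier curves and a confidence interval for the median. Statistical issues states the DFS hypotheses without naming a test.

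**Not found.** An accrual period, a last-entry date, a minimum follow-up, a data cut-off, or a statement of what 28 March 2024 marks.

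**The concern.** A five-year calendar window can give five years of follow-up only to patients entered on its first day. With staggered entry, the window and a 5-year endpoint fit together only if the end date is something other than the end of follow-up, and the plan does not say that it is.

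What is at stake depends on what the date means. If it closes follow-up, the 5-year rate cannot be estimated usefully, the 5-year visit falls outside the trial for nearly everyone, and the comparison has fewer events than full follow-up would give. If it closes accrual, the endpoint is intact, but the date line is misleading and the time of the primary analysis is still unset.

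A smaller matter goes with this. Two tests are named, neither is assigned to DFS, and the median survival time that the Abstract plans to report is unlikely to be reached.

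**Working it through.** **1. Window.** 28 March 2019 to 28 March 2024 is 1,827 days, exactly five calendar years. A patient entered *x* years after the start has at most 5 − *x* years of follow-up if the end date closes follow-up. Only *x* = 0 gives five years.

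**2. Plan's own figures.** 2 × 157 / 0.9 = 348.9, which matches the stated 348 to rounding. The 157 itself does not follow from the stated inputs: 2 × (1.960 + 1.282)² / 0.1² gives 2,102 per group. That is a separate sample-size matter. Here 157 per arm is simply taken as given.

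**3. Assumptions for the illustration (not in the documents).**
- The end date closes follow-up.
- DFS is exponential.
- Accrual is uniform over *A* years.
- 157 per arm are analysed.
- The 10% effect is an absolute difference at five years. Statistical issues does not say absolute or relative, and gives no control rate.

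**4. Formulas.**
- Hazard: λ = −ln(S₅)/5
- P(event) = 1 − [exp(−λ(T−A)) − exp(−λT)]/(λA), with T = 5
- Events *d* = 157 × (P₀ + P₁)
- HR = ln(S₅ statin)/ln(S₅ control)
- Schoenfeld power = Φ(√d·|ln HR|/2 − 1.96)

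Worked case, 80% v 90%: λ₀ = 0.04463, λ₁ = 0.02107, HR = 0.472, ln HR = −0.750. Full five years: d = 157 × (0.20 + 0.10) = 47.1, and Φ(√47.1 × 0.750/2 − 1.96) = Φ(0.615) = 73%. With A = 2: P₀ = 0.1632, P₁ = 0.0808, d = 38.3, power 64%.

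| 5-year DFS | Full 5 years | A = 1 | A = 2 | A = 3 | A = 4 |
|---|---|---|---|---|---|
| 70% v 80%, events (power) | 78.5 (55%) | 71.6 (51%) | 64.5 (47%) | 57.1 (43%) | 49.3 (38%) |
| 80% v 90%, events (power) | 47.1 (73%) | 42.8 (69%) | 38.3 (64%) | 33.7 (59%) | 29.1 (53%) |
| 85% v 95%, events (power) | 31.4 (90%) | 28.4 (87%) | 25.4 (83%) | 22.4 (78%) | 19.2 (72%) |

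Relative reading, 10% fewer recurrences (80% v 82%): HR = 0.889. Power is about 6–7% with full follow-up or with 1 to 3 years of accrual, and the loss is about 1 point.

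**5. Numbers at risk, both arms, 80% v 90%.** 157 × G(t) × [exp(−λ₀t) + exp(−λ₁t)], with G(t) = min(1, (5−t)/A):

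| Month | A = 1 | A = 2 | A = 3 |
|---|---|---|---|
| 48 | 276 | 138 | 92 |
| 54 | 136 | 68 | 45 |
| 59 | 22 | 11 | 7 |
| 60 | about 0 | about 0 | about 0 |

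The expected Greenwood 95% CI half-width for the arm difference at 59 months is 9.0/10.9/12.8 points for A = 1/2/3, against 7.8 at 60 months with complete follow-up.

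**6. Median.** Exponential median = 5 ln 2/(−ln S₅): 9.7, 15.5 and 32.9 years at 70%, 80% and 90% 5-year DFS. None lies within five years.

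**The case against.** **The lost follow-up rests on one reading of one line.** The case form gives each patient a 5-year visit and the endpoint is 5-year DFS. Together these suggest 60 months per patient, with analysis after the last such visit. This stands. A reader might infer that the plan will truncate follow-up, but no text calls 28 March 2024 the cut-off. What is established is a conflict on the plain reading, and a missing statement on either reading.

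**Kaplan-Meier and log-rank methods handle administrative censoring.** This also stands. A reader might infer bias, but nothing in the plan makes censoring at a calendar date depend on prognosis. The harm would be fewer events and an unusable 60-month estimate.

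**The illustration does not bound the loss.** Correct. Four years of accrual costs about 17 to 21 points in the three absolute scenarios, and the relative reading costs about 1. Nor should the gap between the stated 90% power and the full-follow-up figures be put down to the dates, since it exists before any truncation.

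**The log-rank test is plainly meant for DFS.** It is the natural reading. A reader might infer that a t-test is planned on DFS, because the sample size uses one. But the sentence naming the t-test gives no variable, and it could serve the lipid and liver measurements. The missing label alone is only missing detail.

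**Conclusion.** The point holds as a conflict between the stated dates and the stated endpoint, together with an unstated accrual period and data cut-off. On the plain reading, only first-day entrants could reach 60 months, so the plan as written could not deliver its own 5-year rate. If the dates are the accrual window, the endpoint survives and the date line needs correcting.

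The power figures are illustrative. They depend on the end date closing follow-up, exponential DFS, uniform accrual, an assumed control rate and an absolute 10-point effect. Confidence is high for the conflict and the missing cut-off, and not for the amount of follow-up lost. This should be fixed, but the documents do not show that the primary comparison is invalid.

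**What to change.** **1. State the accrual period and the data cut-off, and reconcile them with the endpoint in one of three ways.**
- *Follow every patient to 60 months:* set the cut-off at 60 months after the last randomisation. This keeps 5-year DFS and the visit schedule. The cost is later closure by the length of accrual. Counting all follow-up to that date (the events formula above with T = 5 + A), 80% v 90% gives 51.3/55.5/59.5 events and 77/80/83% power for A = 1/2/3.
- *The dates are the accrual window:* say so and give the cut-off. This is a wording change.
- *28 March 2024 is the cut-off:* make the primary endpoint time-to-event DFS, restate expected events and power for the actual follow-up, and claim no 5-year rate. Report Kaplan-Meier rates at one time, prespecified from the actual accrual and with adequate numbers at risk. This needs no new patients or visits. The cost is losing the 5-year rate, less favourable stated power, and a smaller difference at an earlier time: under 80% v 90%, the 10 points at 60 months are exp(−4λ₁) − exp(−4λ₀) = 0.919 − 0.837, or 8.3 points, at 48 months.

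**2. Name the log-rank test as the primary DFS test.** Stratify it by molecular subtype if the stratified blocked randomisation that the plan describes is used. Keep the t-test for continuous variables such as lipids. Report a hazard ratio and Kaplan-Meier rates, each with a 95% CI, beside the median. The cost is a few lines of text.

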#### **Statistical issues:**

### Primary outcomes:

The research question is whether statins can benefit breast cancer patients with dyslipidemia (low and medium risk of ASCVD). The main endpoint was DFS. A review of the literature suggests that simvastatin reduced the recurrence rate of breast cancer by 10%. The investigator would like to be able to detect a difference of 10% or more in DFS change between the two groups. How many patients are required in each group at  $\alpha$  (two-sided) = 0.05;  $\beta$  = 0.10, power = 0.90.

1. Null Hypothesis: For breast cancer patients with dyslipidemia (low and medium risk of ASCVD) under endocrine therapy, whether statin used is the same in DFS.
2. Alternative Hypothesis (two-sided): For breast cancer patients with dyslipidemia (low and medium risk of ASCVD) under endocrine therapy, whether statin used is different in DFS.
3. Effect size=0.1(10%\*2)
4. Standard deviation of CTC=1
5. Standardized effect size=effect size/standard deviation=0.1/1=0.1
6.  $\alpha$  (two-sided) = 0.05;  $\beta$  = 0.10, power = 0.9
7. Based on Appendix 6A from the text book, the estimated sample size is 157 in each group.
8. Ultimate sample size =  $2*157/0.9= 348$

Looking across from a standardized effect size of 0.10 in the leftmost column in Table 6A and down from  $\alpha$  (two-side) =0.05 and  $\beta$  = 0.10 is the required sample size of 157patients in statins group and control group. With 10% dropout the final sample size is 348[14].

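### The only interval estimate planned is for the median survival time, which does not measure the 5-year DFS rate or its 10% target and is likely to be unavailable within 5 years

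*Combined protocol and SAP*

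**What the plan says.** The endpoint is fixed in time. The Abstract states "The main endpoint was 5 years DFS", and the overview of the design repeats it. The Measurements section has "The primary outcome: DFS (disease free survival) rate", with the OS rate as the secondary outcome.

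The target is given under Statistical issues, Primary outcomes: "The investigator would like to be able to detect a difference of 10% or more in DFS change between the two groups".

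The survival analysis appears only in the Abstract: "Log rank test was used with survival curve based on Kaplan Merier method and 95% confidence interval of median survival time". That sentence does not say whether the median is of DFS or OS. The same section also says "For statistical analysis, t-test will be used between two different groups", without naming the variable to be tested. The Primary outcomes section covers hypotheses and sample size only. Nowhere does the plan name a 5-year DFS estimate with an interval, a between-arm difference with an interval, or a hazard ratio.

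Two statements bound the follow-up. The last entry on the Appendix record form is "5 year follow-up: date", and the Abstract states "This is a randomized clinical trial from March 28st 2019 to March 28st 2024".

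**The concern.** Two separate things are wrong with the median here.

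First, it is the wrong quantity. The plan asks how far apart the arms are in the proportion disease-free at 5 years. A median is the time by which half have had an event. Even a well-estimated median in each arm would not tell a reader whether a 10% difference in DFS had been met, ruled out or left open.

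Second, it may not be estimable. The Kaplan-Meier median is defined only if the curve drops to 50% or below while patients are under observation. A finite upper confidence limit needs the upper confidence band to drop that far too.

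At stake is the main result. If the plan is followed to the letter, the report could contain a log-rank p-value and two curves, but no prespecified interval for the endpoint that the trial defined.

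**Working it through.** **Inputs from the documents.** Endpoint: 5-year DFS (Abstract, Measurements). Target: 10% (Primary outcomes). Last visit: 5 years (Appendix). Calendar: 28 March 2019 to 28 March 2024 (Abstract). Arm size after dropout: 157 (Primary outcomes). No control DFS, hazard ratio, event count or median is stated, so the plan has no figure of its own to reproduce on this point. The 157 is used below only as an arm size; its derivation is a separate matter.

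**Step 1: where the median falls.** Assume a constant hazard λ = −ln(S5)/5, where S5 is 5-year DFS. The median is ln 2/λ = 5 × ln(0.5)/ln(S5).

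| Assumed 5-year DFS | Calculation | Median (years) |
|---|---|---|
| 50% | 5 × 0.693/0.693 | 5.0 |
| 60% | 5 × 0.693/0.511 | 6.8 |
| 70% | 5 × 0.693/0.357 | 9.7 |
| 80% | 5 × 0.693/0.223 | 15.5 |
| 90% | 5 × 0.693/0.105 | 32.9 |

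Any assumed 5-year DFS above 50% places the median beyond the last visit.

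**Step 2: the median does not translate into the target.** From the same table, a 10-point gap in 5-year DFS corresponds to a gap in medians of 9.7 − 6.8 = 2.9 years (60% against 70%), 15.5 − 9.7 = 5.8 years (70% against 80%) or 32.9 − 15.5 = 17.4 years (80% against 90%). One target gives three very different median differences.

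**Step 3: how often the median and its upper limit would be obtained.** Simulation with 157 patients in an arm, exponential times, 2,000 runs, log-log confidence limits and complete 5-year follow-up:

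| True 5-year DFS | Curve reaches 50% | Upper 95% limit finite |
|---|---|---|
| 40% | 99.4% | 73.4% |
| 45% | 89.8% | 25.4% |
| 50% | 49.5% | 2.7% |
| 55% | 9.6% | 0.1% |
| 60% | 0.6% | 0.0% |
| 70% or more | 0.0% | 0.0% |

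Suppose instead that enrolment is uniform over 2 or 3 years inside the 5-year calendar (an assumption). The curve then reaches 50% in 5.6% or 6.9% of runs at a DFS of 60%, and in 1.0% or 1.8% at 70%. A finite upper limit appears in 0.2% of runs in each of these cases.

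**Step 4: what the rate difference would give.** With complete 5-year follow-up, the 95% half-width is 1.96 × √[(p(1−p) + q(1−q))/157], where p is control DFS and q = p + 0.10.

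- 60% against 70%: 1.96 × √(0.45/157) = 10.5 points
- 70% against 80%: 1.96 × √(0.37/157) = 9.5 points
- 80% against 90%: 1.96 × √(0.25/157) = 7.8 points

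The difference can be estimated in every case, although the interval is wide relative to 10 points.

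**Step 5: the calendar.** The stated dates span exactly 5 years. If they include enrolment, a patient entered m months after the start has at most 60 − m months of follow-up, so only those entered at the very start reach year 5. The half-widths in step 4 would then not apply.

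**Step 6: meaning of 10%.** The Primary outcomes section moves from a 10% reduction in recurrence to a 10% difference in DFS without saying whether this is relative or absolute. Take an assumed control DFS of 80% and count every event as a recurrence. A 10% relative reduction takes recurrence from 20% to 18%, a gap of 2 points; an absolute reading gives 10 points.

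**The case against.** The log-rank test is valid whether or not a median is reached. The Kaplan-Meier curve is planned, and the DFS and OS rates are named as outcomes. Where patients remain at risk, a 5-year rate can be read from that curve. This stands. The endpoint is not left unaddressed: what is missing is a prespecified interval for the rate and for the between-arm difference.

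A reader might infer that the trial is bound to report medians not reached in both arms. The documents do not support that. They give no control DFS. The assumed subtype mix of about 80% luminal (32.73% + 47.01%) comes without outcome figures, and eligibility requires surgery but sets no stage limit. The conclusion is conditional on 5-year DFS.

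A reader might also infer that a median needs events in half the patients. Under censoring the rule is that the curve must fall to 50%, which can happen with fewer events. The staggered-entry results in step 3 show this, though the effect is small.

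Finally, a reader might take the remedy to be a change of wording alone. It is not, if the stated dates include enrolment. A 5-year rate would then rest on almost no patients and be no better supported than the median.

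It can also be said that a hazard ratio goes beyond what a fixed-time endpoint needs. But it is the natural companion to the planned log-rank test, and it remains usable if few patients reach year 5.

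**Conclusion.** The point holds and should be acted on. The mismatch between the interval planned (a median time) and the endpoint and target (a 5-year rate and a 10% difference) is plain from the text and does not depend on any event rate.

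That the interval will be unavailable is likely but not certain, and it rests on an assumed DFS. Under a constant hazard, the median lies beyond the form at any 5-year DFS above 50%. With 157 per arm and full follow-up, a finite upper limit was obtained in only 2.7% of runs even at a DFS of exactly 50%; it was obtained in most runs only at about 40%.

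The alternative can be estimated, with a half-width of about 7.8 to 10.5 points over the assumed control range of 80% down to 60%, provided each patient is followed for 5 years. Whether that condition is met depends on what the trial dates cover, which the documents leave open.

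**What to change.** - In the Abstract and in the Statistical issues section, replace the interval for the median with the Kaplan-Meier 5-year DFS in each arm with 95% CI, the between-arm difference with 95% CI, and the hazard ratio with 95% CI to accompany the log-rank test. Do the same for OS. Give a median only if it is reached.
- State whether the 10% is an absolute difference in 5-year DFS or a relative reduction, so that the interval can be read against it.
- Reconcile the trial dates with the endpoint. Either state that the dates cover enrolment only and that each patient is followed to the 5-year visit, or report the rate at the latest time with adequate numbers at risk in both arms and rely on the hazard ratio for the overall comparison.

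Cost: a small amount of extra analysis from the same Kaplan-Meier data, with no new measurements, and a clarification of the follow-up dates. If the dates do include enrolment, following everyone to year 5 means extending follow-up beyond March 2024, which is a real cost.
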